6.0 ENDPOINT ASSESSMENT

6.1 Solid tumors

- 6.1.1 Response will be evaluated using the modified Response Evaluation Criteria in Solid Tumors, based on RECIST v1.1.³⁵
- 6.1.2 Clinical evaluation and tumor assessments will be performed as indicated in Table 6, based on physical examination and radiologic evaluation.
- 6.1.3 Any lesion that has been previously treated with radiotherapy should be considered as a non-target lesion. However, if a lesion previously treated with radiotherapy has clearly progressed since the radiotherapy, it can be considered as a target lesion.
- 6.1.4 Definitions for measurable and non-measurable lesions, and criteria for response, should be based on RECIST v1.1.

6.1.5 Measurable Disease

Measurable lesions are defined as those that can be accurately measured in at least one dimension (longest diameter to be recorded) as ≥ 20 mm (≥ 2 cm) by chest x-ray or as ≥ 10 mm (≥ 1 cm) with CT scan, MRI, or calipers by clinical exam. All tumor measurements must be recorded in millimeters (or decimal fractions of centimeters).

6.1.6 Non-measurable Disease

All other lesions (or sites of disease), including small lesions (longest diameter < 10 mm [< 1 cm] or pathological lymph nodes with ≥ 10 to < 15 mm [≥ 1 to < 1.5 cm] short axis), are considered non-measurable disease. Bone lesions, leptomeningeal disease, ascites, pleural/pericardial effusions, lymphangitis cutis/pulmonitis, inflammatory breast disease, and abdominal masses (not followed by CT or MRI), are considered as non-measurable.

Note: Cystic lesions that meet the criteria for radiographically defined simple cysts should not be considered as malignant lesions (neither measurable nor non-measurable) since they are, by definition, simple cysts.

'Cystic lesions' thought to represent cystic metastases can be considered as measurable lesions, if they meet the definition of measurability described above. However, if non-cystic lesions are present in the same patient, these are preferred for selection as target lesions.

6.1.7 Response criteria

- **Complete Response (CR)** - Disappearance of all target lesions. Any pathological lymph nodes (whether target or non-target) must have reduction in short axis to < 10 mm.
- **Partial Response (PR)** - At least a 30% decrease in the sum of the diameters of target lesions, taking as reference the baseline sum diameters.
- **Objective Response Rate** – the sum of complete responses and partial responses
- **Progressive Disease (PD)** - At least a 20% increase in the sum of diameters of target lesions, taking as reference the smallest sum on study (this includes the baseline sum if that is the smallest on study). In addition to the relative increase of 20%, the sum must also demonstrate an absolute increase of at least 5 mm. (Note: the appearance of one or more new lesions is also considered progression.)
- **Stable Disease (SD)** - Neither sufficient shrinkage to qualify for PR nor sufficient increase to qualify for PD, taking as reference the smallest sum of diameters while on study.

6.2 Lymphoma

- 6.2.1 Response will be evaluated, using the Lugano classification for assessment of Lymphoma.³⁶ See Appendix C for specific response assessment criteria.
- 6.2.2 Clinical evaluation and tumor assessments will be performed periodically, as shown in Table 6, based on evaluation of spleen and liver, physical examination for superficial disease and B symptoms, radiologic evaluation, and appropriate laboratory studies.
- 6.2.3 A lesion is categorized based on the location as either a nodal lesion or an extranodal lesion if it is located in organs other than lymph nodes or nodal mass, but including spleen and liver.
- 6.2.4 All tumor lesions/lymph nodes will be categorized as measurable or non-measurable as follows:
- Measurable nodal and extranodal lesions:
A lesion will be called measurable if it can be measured accurately in 2 perpendicular dimensions and:
 - For nodal lesion, if the long axis is >15 mm, regardless of the length of the short axis
 - For extranodal lesion, if the long and short axes are ≥ 10 mm.Patients should have at least one measurable nodal lesion greater than 20 mm in the long axis.
In cases where the patient has no measurable nodal lesions greater than 20 mm in the long axis at screening, then the patient must have at least one measurable extranodal lesion.
- 6.2.5 Classification of lymph nodes
- Lymph nodes are classified according to their size and/or relationship to the disease:
 - A lymph node meeting the measurability requirement, but with long axis > 15 mm (e.g. short axis cannot be measured accurately) will constitute a non-measurable nodal lesion.
 - A lymph node not meeting the measurability criteria, but with a size of 11 mm to 15 mm in the long axis and >10 mm in the short axis will be checked for relationship to disease:
 - If it is thought to be disease related, it will constitute a non-measurable nodal lesion
 - If it is not thought to be disease related, it will constitute an abnormal lymph node, but not a lesion.All other lymph nodes will be considered normal and will not constitute nodal lesions.
- 6.2.6 Criteria for normalization of lesions
- The normalization of lesions is defined as follow:
 - A measurable nodal lesion must become ≤ 15 mm in long axis to be considered normalized.
 - A non-measurable nodal lesion must decrease to ≤ 10 mm in the short axis and be ≤ 15 mm in long axis to be considered normalized.
 - An extranodal lesion must disappear completely (assigned a size of 0 mm x 0 mm) to be considered normalized.

6.3 Immune-related RECIST (irRECIST)

- 6.3.1 In addition to above, tumor response for both solid tumors and lymphoma will be assessed by the irRECIST for investigational purposes, not assessment of primary objective.³⁷ In RECIST v1.1, the appearance of new lesions indicates PD. However, in irRECIST, new measurable lesions are incorporated in the tumor burden, which is used to determine irPD, immune-related partial response (irPR), and immune-related complete response (irCR). New nonmeasurable lesions preclude irCR. Under RECIST v1.1, there is no confirmation for PD. Under irRECIST, responses and irPDs must be confirmed by consecutive scans at least 4 weeks apart, assuming no clinical deterioration. We will define immune-related clinical benefit rate as immune-related stable disease (irSD), irPR, or irCR.

Table 6: Immune-related Response Evaluation Criteria: Overall Response

Tumor Burden (Baseline and New)	Non-Target Lesions (Baseline and New)	Response
Disappearance of non-nodal lesions. All pathologic lymph nodes <10 mm (short axis)	Disappearance of non-nodal lesions. All pathologic lymph nodes < 10 mm (short axis)	irCR
≥30% decrease from baseline	Any	irPR
≥20% increase from nadir and at least 5 mm	Any	irPD
Neither sufficient decrease to qualify for PR, nor sufficient increase to qualify for PD	Any	irSD
Disappearance of all non-nodal lesions. All pathologic lymph nodes <10 mm	Any other than disappearance of all non-nodal lesions and reduction of pathologic lymph nodes <10 mm	irPR
Not all evaluated	Any	irNE

irCR = immune-related complete response; irPD = immune-related progressive disease; irPR = immune-related partial response; irNE = immune-related not evaluable; irSD = immune-related stable disease;

-Tumor burden is the sum of single diameters (short axis for nodal lesions, longest diameter for other lesions) for the target lesions. In subsequent scans, the diameters of new measurable lesions are added to the tumor burden.

-Best overall response based on 2 consecutive measurements at least 4 weeks apart.

6.4 Primary Endpoint

The primary objective is to identify maximum tolerated dose (MTD) for the combination treatment of nivolumab and veliparib.

The MTD will be defined as the highest dose that causes dose-limiting toxicities (DLTs) in <2 of 6 patients and is determined for this study..

6.5 Secondary Endpoints

6.5.1 Secondary endpoints include the number, frequency, and severity of adverse events (as defined by the NCI Common Terminology Criteria for Adverse Events or CTCAE version 4.03) will be recorded.

6.5.2 To evaluate the efficacy of treatment with nivolumab and veliparib in this population by objective response rate (ORR, defined as partial response (PR) + complete response (CR)), clinical benefit rate (CBR, defined as stable disease (SD) for ≥12 weeks, PR, + CR), and Progression Free Survival (PFS, defined as the time from treatment initiation to documented disease progression) using RECIST criteria v1.1 or the Lugano 2014 classification for assessment of Lymphoma³⁶.

For the preliminary efficacy analysis, ORR and other measures will be computed separately for patients with and those without genetic mutations, at the first imaging (8 weeks). Preliminary efficacy will be evaluated by RECISTv 1.1. As exploratory analysis, irRECIST will be used to obtain preliminary efficacy as well. All ORR will use the first imaging time point whether RECIST or irRECIST.

- 6.5.3 To evaluate efficacy of treatment with nivolumab and veliparib in this population by ORR, CBR, and immune-related PFS (irPFS) using irRECIST criteria.
- 6.5.4 To evaluate Overall Survival (OS) in this population at 3 years from the start of treatment. OS is defined as the time from treatment initiation until death due to any cause.
- 6.5.5 To evaluate the proportion of patients alive and progression free at 24 weeks in this population.

6.6 Exploratory Endpoints

- 6.6.1 Biomarkers predictive of response include assessment of tissue-based immunohistochemical expression of PD-L1; TILs; peripheral T cell subpopulations; changes in tissue and peripheral T cell receptor sequencing, HLA genotype, and immune-related candidate gene signatures at baseline.
- 6.6.2 To demonstrate the pharmacodynamic effects of veliparib and nivolumab on biomarkers including PD-L1, TILs, T cell subpopulations, and T cell receptor genotype.

7.0 ADVERSE EVENTS

This study will be conducted in compliance with the Data Safety Monitoring Plan (DSMP) of the Robert H. Lurie Comprehensive Cancer Center of Northwestern University (please refer to Appendices for additional information). The level of risk attributed to this study requires high level monitoring, as outlined in the DSMP. In addition, the study will abide by all safety reporting regulations, as set forth in the Code of Federal Regulations.

7.1 Adverse Event Monitoring

Adverse event data collection and reporting, which are required as part of every clinical trial, are done to ensure the safety of subjects enrolled in the studies as well as those who will enroll in future studies using similar agents. Adverse events are reported in a routine manner from the time of consent until 30 days after treatment discontinuation (100 days for SAE's) at scheduled times during a trial (see Section 5 for time points). In addition, certain adverse events must be reported in an expedited manner to allow for optimal monitoring and patient safety and care.

All patients experiencing an adverse event, regardless of its relationship to study drug, will be followed until:

- the adverse event resolves or the symptoms or signs that constitute the adverse event return to baseline;
- any abnormal laboratory values have returned to baseline;
- there is a satisfactory explanation other than the study drug for the changes observed; or
- death

7.2 Definitions & Descriptions

7.2.1 Adverse Event

An adverse event (AE) is any untoward medical occurrence in a patient receiving study treatment and which does not necessarily have a causal relationship with this treatment. An AE can therefore be any unfavorable and unintended sign

(including an abnormal laboratory finding), symptom, or disease temporally associated with the use of an experimental intervention, whether or not related to the intervention.

Recording of AEs should be done in a concise manner using standard, acceptable medical terms. In general, AEs are not procedures or measurements, but should reflect the reason for the procedure or the diagnosis based on the abnormal measurement. Preexisting conditions that worsen in severity or frequency during the study should also be recorded (a preexisting condition that does not worsen is not an AE). Further, a procedure or surgery is not an AE; rather, the event leading to the procedure or surgery is considered an AE.

If a specific medical diagnosis has been made, that diagnosis or syndrome should be recorded as the AE whenever possible. However, a complete description of the signs, symptoms and investigations which led to the diagnosis should be provided. For example, if clinically significant elevations of liver function tests are known to be secondary to hepatitis, "hepatitis" and not "elevated liver function tests" should be recorded. If the cause is not known, the abnormal test or finding should be recorded as an AE, using appropriate medical terminology (e/g/ thrombocytopenia, peripheral edema, QT prolongation).

7.2.2 Severity of AEs

All non-hematologic adverse events will be graded according to the NCI Common Terminology Criteria for Adverse Events (CTCAE) version 4.03. The CTCAE v4.03 is available at <http://ctep.cancer.gov/reporting/ctc.html>

If no CTCAE grading is available, the severity of an AE is graded as follows:

- Mild (grade 1): the event causes discomfort without disruption of normal daily activities.
- Moderate (grade 2): the event causes discomfort that affects normal daily activities.
- Severe (grade 3): the event makes the patient unable to perform normal daily activities or significantly affects his/her clinical status.
- Life-threatening (grade 4): the patient was at risk of death at the time of the event.
- Fatal (grade 5): the event caused death.

7.2.3 Serious Adverse Events (SAEs)

All SAEs, regardless of attribution, occurring from time of signed informed consent, through 100 days after the last administration of study drug, must be reported upon discovery or occurrence.

An SAE is defined in regulatory terminology as any untoward medical occurrence that:

- **Results in death.**
If death results from (progression of) the disease, the disease should be reported as event itself.
- **Is life-threatening.**
The patient was at risk of death at the time of the event; it does not refer to an event that hypothetically might have caused death if it were more severe.
- **Requires in-patient hospitalization or prolongation of existing hospitalization for ≥ 24 hours.**
- **Results in persistent or significant disability or incapacity.**
- **Is a congenital anomaly/birth defect.**
- **Is an important medical event.**
Any event that does not meet the above criteria, but that in the judgment of the investigator jeopardizes the patient, may be considered for reporting as a

serious adverse event. The event may require medical or surgical intervention to prevent one of the outcomes listed in the definition of "Serious Adverse Event".

For example: allergic bronchospasm requiring intensive treatment in an emergency room or at home; convulsions that may not result in hospitalization; development of drug abuse or drug dependency.

7.2.4 Exceptions to AE and SAE definitions

Generally speaking, any adverse event that results in hospitalization or prolonged hospitalization should be documented and reported as an SAE, as described above. Likewise, any condition responsible for surgery should be documented as an AE if the condition meets the criteria for an AE. However, for the purposes of this study, neither the condition, hospitalization, prolonged hospitalization, nor surgery are reported as AEs or SAEs under the following circumstances:

- Hospitalization or prolonged hospitalization is for a diagnostic or elective surgical procedure for a preexisting condition. Surgery should not be reported as an outcome of an adverse event if the purpose of the surgery was elective or diagnostic and the outcome was uneventful.
- Hospitalization or prolonged hospitalization is required to allow efficacy measurement for the study.
- Hospitalization or prolonged hospitalization is required for study-directed therapy of the target disease of the study, unless it is a worsening or increase in frequency of hospital admissions as judged by the principal investigator.
- Hospitalization or prolonged hospitalization is due to social reasons (i.e. awaiting transport home).
- Pregnancy is not considered a serious adverse event, any patients who become pregnant during the study should discontinue the study immediately. Patients should be instructed to notify the investigator if it is determined after completion of the study that they become pregnant either during the treatment phase of the study or within 30 days or five half-lives after the treatment period, whichever is longer.

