NOTE: *Patients with stable brain mets which have been treated are eligible. Patients with suspected symptoms of CNS metastasis should undergo CNS imaging at the time of screening to rule out active metastasis.*
- 3.2.13 Patients who have had a prior severe infusion reaction to a monoclonal antibody are not eligible.
- 3.2.14 Patients are not eligible who have a history of or active autoimmune disease within the past 3 years with the following exceptions:
- Vitiligo or alopecia
 - Hypothyroidism on stable doses of thyroid replacement therapy
 - Psoriasis not requiring systemic therapy within the past 3 years
- 3.2.15 Patients with a history of primary immunodeficiency disease or tuberculosis are not eligible.
- 3.2.16 Patients who have an uncontrolled current illness including, but not limited to any of the following, are not eligible:
- Uncontrolled pulmonary, renal, or hepatic dysfunction
 - Ongoing or active infection requiring systemic treatment including hepatitis B and hepatitis C
 - Known active or chronic viral hepatitis or human immunodeficiency virus (HIV)
 - Psychiatric illness/social situations that would limit compliance with study requirements
 - Clinically significant gastrointestinal disease or digestive dysfunction compromising absorption of veliparib
 - Any other illness or condition that the treating investigator feels would interfere with study compliance or would compromise the patient's safety or study endpoints
- 3.2.17 Female patients who are pregnant or nursing are not eligible.
- 3.2.18 Patients with a prior diagnosis of cancer must not have received treatment in the last 3 years prior to registration.
NOTE: treatments used as a recurrence prevent are eligible.
NOTE: *Patients with a history of completely resected non-melanomatous skin carcinoma or successfully treated in situ carcinoma are eligible.*
- 3.2.19 Patients must not have a history of prior stroke, transient ischemic attack (TIA), pulmonary embolism, or untreated deep vein thrombosis.
NOTE: *Patients may be eligible if they have received at least 3 months of anticoagulation for a deep vein thrombosis.*

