4.3.1 Definition of DLT (Dose limiting toxicity)

Toxicity will be assessed using the National Cancer Institute (NCI) Common Toxicity Criteria for Adverse Events (CTCAE), version 4.03 unless otherwise specified. A DLT is defined as an AE or abnormal laboratory value assessed as at least possibly related to the study medication, occurs ≤ 28 days following the first dose of veliparib and nivolumab and meets any of the criteria listed below. Whenever a patient experiences toxicity that fulfills the criteria for a DLT, treatment with the study drug combination will be interrupted until resolution to ≤ Grade 1 or baseline, and the toxicity will be followed up until resolution. All adverse events specified below will be DLT's except those that are clearly and incontrovertibly due to extraneous causes.

The following events will be considered DLT's:

1. Grade ≥ 3 non-hematologic toxicities that represent at least a 2-grade increase from baseline with the following exceptions:
 - a. Nausea, vomiting, and diarrhea lasting ≤48 hours
 - b. Electrolyte abnormalities resolving within ≤24 hours
 - c. Hypersensitivity reactions
 - d. Alopecia
2. Grade 4 thrombocytopenia (platelets < 25.0 x 10⁹/L)
3. Grade 3 thrombocytopenia with bleeding (platelets <50.0 x 10⁹/L)
4. Grade 4 neutropenia (ANC < 0.5 x 10⁹/L)
5. Grade 3 febrile neutropenia with fever lasting for > 7 days
6. Grade 4 febrile neutropenia of any duration
7. Dosing delay due to toxicity for > 14 consecutive days from the date nivolumab or veliparib is due.

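### Section 7.2.4 excludes the condition itself, not only the hospital stay, from AE and SAE reporting, which conflicts with 7.2.1 for a preexisting condition that worsens on treatment

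*Combined protocol and SAP*

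**What the plan says.** Section 7.2.1 defines an AE. On preexisting disease it says: "Preexisting conditions that worsen in severity or frequency during the study should also be recorded". It adds that one that does not worsen is not an AE, and that a procedure or operation is not itself an AE; the event that led to it is.

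Section 7.2.4 opens with the general rule that "any adverse event that results in hospitalization or prolonged hospitalization should be documented and reported as an SAE". It then says that a condition responsible for surgery is documented as an AE when it satisfies the AE criteria. Next it makes a study-specific exception: "neither the condition, hospitalization, prolonged hospitalization, nor surgery are reported as AEs or SAEs under the following circumstances". The first circumstance listed is: "Hospitalization or prolonged hospitalization is for a diagnostic or elective surgical procedure for a preexisting condition". The item on study-directed therapy of the target disease is qualified: "unless it is a worsening or increase in frequency of hospital admissions as judged by the principal investigator". The preexisting-condition item carries no such qualifier. A further item covers stays due to social reasons.

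Sections 2.2.1 and 6.5.1 make the counts, rates and grades of AEs a secondary endpoint. Sections 7.3.3.1, 7.3.3.3 and 7.3.3.4 tie SAE status to reporting to the QAM and the two manufacturers within 24 hours, to DMC review and to FDA reporting.

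**The concern.** An exception of this kind normally stops an elective or administrative stay from making an event serious. This one goes further, because it names the condition among the things not reported, and it covers AEs as well as SAEs. A coordinator who follows 7.2.4 literally would leave out an event that 7.2.1 says to record.

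The case is foreseeable in this population. Section 3.2.14 admits patients with vitiligo or alopecia, with hypothyroidism on stable replacement, and with "Psoriasis not requiring systemic therapy within the past 3 years". Section 3.1.9 admits transaminases up to 5 times the upper limit of normal. Worsening of these baseline problems is what a safety review of a checkpoint inhibitor would want to see. Section 8.3.1 states that no trial of veliparib with nivolumab was known to have been reported, so this trial's AE record is a main source of information on the combination.

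**Working it through.** No arithmetic applies, and the plan states no figure to reproduce. The check sets the sections side by side for one case: a preexisting condition worsens after treatment starts, and the patient is admitted for a diagnostic work-up or an elective operation for it.

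| Provision | Result for this case |
|---|---|
| 7.2.1, worsened preexisting conditions | Recorded as an AE |
| 7.2.1, procedures and surgery | The event behind the procedure is the AE |
| 7.2.4, opening sentence | An AE leading to hospitalization is an SAE |
| 7.2.4, exception with its first item | Condition, stay and surgery are reported as neither AE nor SAE |
| 7.2.4, qualifier for worsening | Not available; it belongs to the study-directed-therapy item |
| 7.2.5, hepatic abnormality of known cause | Diagnosis recorded as an AE/SAE, expressly including progression of preexisting disease |

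Next, can the words on the condition be read so that the sections agree?

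1. The sentence just before the exception concerns a condition that satisfies the AE criteria. The exception begins with a contrast to that sentence, so it is directed at conditions that would otherwise be AEs.
2. Section 7.2.1 already says that an unworsened preexisting condition is not an AE and that surgery is not an AE. At the AE level, naming the condition in 7.2.4 has an effect only where the condition would otherwise count.
3. The drafters wrote a qualifier for worsening in one item and not in this one. Nothing in 7.2.4 restores the worsened condition.
4. Section 7.2.1 does not refer to 7.2.4, so neither section says which one governs.

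The text therefore contains a conflict for this case. Because the sections give opposite answers, the outcome is undetermined: the event may be omitted, or handled differently from patient to patient. Where the hepatic criteria of 7.2.5 are met, a third provision supports recording.

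The number of events affected would need the frequency of such admissions. The documents do not give it, and no value is assumed here.

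**The case against.** The strongest reply is that 7.2.4 is headed and worded as an exception, and that it can be harmonised with 7.2.1 by taking its preexisting condition to be one that has not worsened. The second sentence of that item gives some support: it says elective or diagnostic surgery with an uneventful course is not to be reported as the outcome of an AE, which presupposes that the AE itself may be on record. AEs are also reviewed at every treatment visit (Table 5) and followed whatever their cause (7.1). This shows that loss is not certain. It does not remove the conflict, because the harmonised reading leaves the mention of the condition with nothing to do at the AE level and has to supply a limit that the text does not state.

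A reader might also infer three stronger points that the documents do not support.

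- *A toxicity disappears when discharge is delayed for social reasons.* A toxicity that caused the admission is reportable under the opening sentence of 7.2.4 and under 7.2.3. The social item is naturally read as covering only the extra days. The wording could be clearer, but it does not set a rule that the toxicity goes unreported.
- *The MTD is in doubt.* Section 4.3.1 says: "A DLT is defined as an AE or abnormal laboratory value", so an omitted AE could in principle be an omitted DLT. But abnormal laboratory values qualify in their own right, escalation is complete, the MTD is established (1.9, 4.1, 10.2), and the modified expansion plan states no DLT-count rule. Nothing indicates that a DLT was missed.
- *Toxicity is biased downward mainly among severe events.* The listed circumstances are elective, diagnostic, efficacy-measurement, study-therapy and social stays. They are not markers of severity.

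**Conclusion.** The point holds in a narrow form. Section 7.2.4 states a rule that is too broad: for a preexisting condition that worsens and leads to a diagnostic or elective surgical admission, it contradicts 7.2.1. Followed literally, it would under-record the AE endpoint and SAE reporting; left unreconciled, it invites inconsistent recording.

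The size cannot be estimated. For scale only, 6 + 6 = 12 patients are planned at 400 mg BID (10.2), so one patient whose event is omitted changes a patient-level AE proportion by 1/12 = 8.3 percentage points. That is not a forecast that any event will be omitted.

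The conclusion rests on the wording alone. It assumes that no separate instruction to sites, such as the data submission guidelines that section 11.4 says are a separate document, already settles the question.

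**What to change.** Amend 7.2.4 to say that a hospitalization, prolonged stay or operation in the listed circumstances does not by itself make an event an AE or SAE. State that any underlying condition that is new or has worsened is still recorded as an AE under 7.2.1, and reported as an SAE if it meets another criterion in 7.2.3. For clarity, say that the social-reasons item covers only the extra days. Add a reference between 7.2.1 and 7.2.4.

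Then check the hospital stays of patients already treated against the revised wording, and add any event that should have been recorded.

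The cost is a short amendment and a limited chart check. A few more AEs or SAEs may be reported. Treatment, dose, sample size and the efficacy analysis do not change.
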